13.4 MEMs Cap Medicine Adherence Data

The coordinating center will be responsible for uploading and maintaining the MEMS cap medicine adherence data. After each patient returns their MEMS cap following their study completions, the study coordinator will mail the track caps in padded envelope to the coordinating center - Seattle Children's Hospital Attn: [name] ([name]). The site coordinator will upload the data will be via the MEMS MAP modem (Aardex Group, Belgium), yielding a record of times and dates that the container was opened. These methods have been used successfully in prior pediatric and AYA adherence studies.^{97,145,146}

13.5 Heart Rate Variability Data

Following a 24-hour recording, a study team member will collect the Actiheart monitor from the patient (either in clinic or while in the hospital). De-identified data from the device will be uploaded into the Actiheart software (CamnTech, Inc), which will be installed on one computer located in the locked office of the study PI. Data will then be transferred to the abovementioned encrypted RedCap database.

13.6 Blood Samples

5 mL whole blood will be collected in a PaxGene (PreAnalytiX GmbH) blood tube at the time of a planned clinical blood draw. These biospecimens will be labeled with the subject's study ID only (no identifying information) and sent to the Seattle Children's Research Lab Services (RLS) Core (Seattle Children's Hospital, Seattle, WA) for storage. De-identified, batched blood samples will be shipped by RLS to the University of California Los Angeles (UCLA) Social Genomics Core Laboratory for analysis.

13.7 Data Collection Procedures/ Internal Site Monitoring plan:

The coordinating center will be responsible for systematic data collection, quality control, and data-management procedures including: (1) oversight of ongoing data collection; (2) rigorous training and ongoing monitoring of adherence to protocols; (3) regular review of questionnaire response rates and missing items to identify and correct problems; (4) verification of all data through computerized data entry systems restricting invalid/out-of-range responses; (5) at minimum monthly meetings and progress reports to provide feedback to study staff concerning difficulties and follow-up to ensure problems are resolved quickly, and (6) yearly on-site monitoring of participating sites.

13.7.1 Survey data:

To optimize collection, all participant surveys will be available by paper or online via the REDCap system, a secure HIPAA-compliant, high-quality data collection tool. The rationale for offering both paper-pencil and electronic versions is based on our prior experience where participants preferred the former,⁹² which in turn facilitated more complete data collection. To ensure primary outcome data, we will offer an abbreviated survey with only the HADS and HUI for those who do not complete all assessments or who request to drop out. To ensure data quality, a RA will review RPCA surveys within 72 hours of their completion for missing fields and call participants to clarify and query/complete individual missing items verbally.

13.7.2 MEMS caps:

One to two weeks following discharge from the initial HCT and the day after any subsequent hospitalizations, an RA will contact the family by phone to review the MEMS-cap system and, where relevant, confirm the MEMS-cap is being used. Where indicated, to identify obstacles and solutions to its use.

13.7.3 Medical record data:

RA's will collect and upload CRF data monthly. To ensure reliability and validity of abstracted medical record data, we will use our current methods for training and quality control, including guided practice abstraction and independent abstraction with reconciliation by a trainer. A 10% random sample will be dual abstracted. A RA assignment will monitor and reconcile case report forms with RedCap data once monthly.

13.7.4 Heart Rate Variability monitors:

Staff investigators and RA's will be trained on recognizing adequate signal acquisition on the Actiheart monitors when the patient initially has the device placed. If there is suboptimal recording identified, the team member placing the device will be able to recognize in real time and make appropriate adjustments to the equipment based on Actiheart user manual suggestions.

13.7.5 Blood Samples:

Following quality assurance testing of suitable mass (Nanodrop ND1000) and integrity (Agilent Bioanalyzer RNA Integrity Score), mRNA will be converted to cDNA (Illumina TruSeq), and >10 million sequence reads will be obtained on an Illumina HiSeq 4000 instrument in the UCLA Neuroscience Genomics Core. Reads will be mapped to the RefSeq human genome (hisat2/stringtie) to estimate gene transcript abundance counts per million mapped reads.

13.8 Safety and Compliance Monitoring

This is a small multisite clinical trial of a supportive care intervention that presents no more than minimal risk. As such, data monitoring will be primarily carried out by the Lead RA at the coordinating site (SCH) and a small, external Data Safety Monitoring Committee (DSMC).

13.8.1 Data and Safety Monitoring Plan

Safety monitoring will be the responsibility of a 4-member Data Safety and Monitoring Committee (DSMC) composed of professionals across the country representing different disciplines and expertise (see table below). All members are independent of the protocol. The committee will be convened at the beginning of the study and then twice annually via conference calls, to provide input and guidance on the study evaluation and intervention protocols, including quality assurance and safety issues related to the protocols, as well as data handling activities. As above, in the event of an unanticipated patient death, the committee may convene an ad-hoc session and/or suspend the study to assess patient risk and/or necessary revisions to the protocol.

13.8.2 Data and Safety Monitoring Committee

Member Name (Title)	Discipline	Research Expertise
[name] (Chief, Division of Pediatric Allergy, Immunology, and Bone Marrow Transplantation, University of California at San Francisco)	Pediatric Hematology/Oncology and Hematopoietic Cell Transplantation	Hematopoietic Stem Cell Transplant, Cancer Control and Supportive Care
[name] (Associate Professor, Depts. of Psychiatry and Behavioral Medicine and Pediatrics, George Washington University School of Medicine)	Pediatric Psychology and Behavioral Medicine	Psychosocial oncology and behavioral intervention development
[name] (Associate Professor and Director of Clinical Research in Adolescent and Young Adult Oncology, Dept. of Social Sciences and Health Policy, Wake Forest University School of Medicine)	Adolescent and Young Adult Psychology	Adolescent and Young Adult health psychology, patient-reported outcomes research
[name] (Committee Chair , Assistant Professor, Dept. of Pediatric Oncology, University of Washington School of Medicine)	Pediatric Hematology/Oncology and Hematopoietic Cell Transplantation	Hematopoietic Stem Cell Transplant

13.8.3 Monitoring study safety.

DSMC members will provide input and feedback to the PI and Co-investigators via e-mail and conference calls, related to (a) accrual rate, (b) study eligibility determination issues, (c) data completion rates including conformance with informed consent requirements, (d) intervention fidelity indicators, (e) adverse events, and (f) compliance with data management procedures. The lead statistician will oversee the summarization of online data to evaluate data completeness and protocol adherence. The Lead CRA will also send monthly reports summarizing recruitment and other site specific data (such as indicators of intervention delivery, occurrence of adverse events, and conformance with IRB requirements).

The committee will also receive information on questionnaire data, presented for the participants overall rather than by study group. This study will not have pre-set stopping rules, but the DSMC will have the option of requesting the data be un-blinded and considering altering the study or stopping the study early. Although the full committee will meet twice-yearly, the chair will be free to assemble the full committee at any time if the chair believes it is important. Because committee members may be located at various sites, the committee meetings may be conducted by phone.

Data safety monitoring for the intervention will focus on assuring that subjects are not experiencing any significant or unexpected distress and that they are satisfied with the intervention components; we will monitor all complaints about the study. We do not anticipate stopping the study early for efficacy or harm, but the DSMC will have the option to consider such action in the event of a highly unexpected result. The DSMC will review the draft questionnaires to be sent to subjects and review any complaints that may be received from patients, family members, clinicians, or others. We do not anticipate any external factors such as findings from ongoing trials that will affect the safety of participants or the ethics of this research study.

13.8.4 Identification, review and report of adverse events and unanticipated problem.

Adverse events information will be collected at all assessment points and recorded on standard forms. We will collect information on all potential types of adverse events. Consistent with NIH, and the sites IRBs policies, adverse events will be promptly reported in writing to the NIH, individual IRBs, and the DSMC chair. The DSMC will modify or stop the study if any such complaints represent a legitimate concern about the study procedures or methods.

13.8.5 Compliance with monitoring requirements.

Compliance with the monitoring plan will be ensured through the Lead RA's close supervision. The Lead RA will hold no less than monthly calls with the sites to monitor recruitment and protocol adherence. Site RAs will gather required information on an ongoing basis and send monthly written reports to Lead RA. The Lead RA will schedule yearly on-site monitoring visits as the coordinate site for data completeness and accuracy. Site RAs will assist in providing on-site monitors with appropriate access to all study related charts and databases during the visit.

13.8.6 Assessment of relevant external factors.

Given the characteristics of the intervention, it is unlikely that a breakthrough result from another study will change the course of this study.

13.8.7 Interim analysis plan.

An interim analysis to assess for safety and missingness will be lead by the study statistician after half of the targeted sample size of participants have reached the primary endpoint. The DSMC will determine a priori stopping rules occurrence of serious events, including (but not limited to) stopping the study for efficacy if interim analysis is significant.

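### Section 13.8.7 allows an efficacy stop on a significant interim result but sets no interim level, boundary or adjusted final level, so the 5% type I error is not assured

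*Combined protocol and SAP*

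**What the plan says.** Section 13.8.7 opens with a limited purpose: "An interim analysis to assess for safety and missingness will be lead by the study statistician". The look comes "after half of the targeted sample size of participants have reached the primary endpoint". It then goes further. "The DSMC will determine a priori stopping rules", and the examples given include "stopping the study for efficacy if interim analysis is significant". No level is attached to the word significant.

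Section 13.8.3 points the other way. It says "This study will not have pre-set stopping rules", has questionnaire data sent to the committee "presented for the participants overall rather than by study group", and adds "We do not anticipate stopping the study early for efficacy or harm". It nevertheless keeps a route to a by-arm look, because "the DSMC will have the option of requesting the data be un-blinded and considering altering the study or stopping the study early".

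Section 11 does not fill the gap. Table 7 in 11.2 assumes a 5% type I error. Section 11.4.1 specifies a Wald t-test on the PRISM coefficient without a level. The Benjamini-Hochberg step in 11.6 is reserved for tests that were not planned in advance, so it does not cover repeated testing of the primary outcome.

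**The concern.** A rule set in advance by the DSMC and a statement that there will be none cannot both guide the trial. If the efficacy clause is live, the primary hypothesis may be tested twice, and the final level has to allow for the first test. Nothing in the plan provides for that. Read literally, the clause permits an interim test at 0.05 followed by a final test at 0.05.

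Two things are at stake. One is the false-positive rate of the single primary test. The other is the size of the reported effect: a trial that stops because an early difference crossed a lenient threshold tends to overstate that difference, and here it could do so on half of the planned evaluable patients. The HADS change also serves as a denominator for the cost-consequence ratios in 11.5.2.

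The timing is loose as well. Half of the target could mean 35 (half of the 70 evaluable) or 45 (half of the 90 randomized).

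**Working it through.** **Inputs from the documents.** HADS SD 6.2, difference 4.2, MCID 3.1, 80% power, 5% type I error, 35 evaluable per arm, 90 randomized (11.2 and Table 7); 1:1 allocation (9.2); one look at half the target (13.8.7).

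**1. Reproduce the plan's own figure.** Patients per arm = 2(z₁₋α/₂ + z₀.₈)² × SD²/Δ².
- Two-sided 5%: 2 × (1.960 + 0.842)² × 6.2²/4.2² = 34.2, so 35.
- One-sided 5%: 27.

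The stated 35 therefore implies a two-sided 5% test, although the sidedness is not written down. Power with 35 per arm is 80.9% by the normal formula and 79.8% by the t-test, which agrees with the plan.

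**2. Overall type I error with one efficacy look.** Let Z₁ and Z₂ be the interim and final statistics and t the information fraction. Under the null they are bivariate normal with correlation √t, and

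overall error = P(|Z₁| > c₁ or |Z₂| > 1.96).

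| Interim two-sided level | t = 35/70 = 0.5 | t = 45/70 = 0.643 |
|---|---|---|
| no efficacy test | 5.00% | 5.00% |
| 0.001 | 5.02% | – |
| 0.005 | 5.19% | – |
| 0.01 | 5.46% | 5.29% |
| 0.02 | 6.09% | – |
| 0.05 | 8.31% | 7.79% |

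A simulation of t-tests at 35 and then 70 patients (400,000 runs, 0.05 at both looks) gave 8.30%. A simulation of the baseline-adjusted model (40,000 runs) gave 8.5% to 8.7%.

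**3. Boundaries that hold 5% at t = 0.5.** For O'Brien-Fleming, c₁ = c₂√2. Solving for 5.0% gives c₂ = 1.977 (p = 0.0480) and c₁ = 2.797 (p = 0.0052). The Pocock boundary is p = 0.0294 at both looks.

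**4. Power of the final test under O'Brien-Fleming.** For 4.2 points, SD 6.2 and 35 per arm, the t-test has 79.8% power at 0.05 and 79.3% at 0.048.

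**5. Exaggeration after a favourable stop on an unadjusted 0.05 look.** The baseline-adjusted model was simulated with a look at 35 evaluable patients. The documents do not give the correlation between baseline and 6-month HADS, so 0, 0.5 and 0.7 are assumed. Two cases are shown: analysis on the 35 alone, and analysis on an assumed 47 after patients already enrolled complete follow-up. The 47 is consistent with the 24 evaluable patients a year in Table 3: 35 + 24 × 0.5 = 47.

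| True effect | Correlation | Chance of favourable stop | Mean estimate at 35 (ratio to truth) | Mean estimate at 47 (ratio to truth) |
|---|---|---|---|---|
| 3.1 | 0 | 29% | 5.52 (1.8) | 4.89 (1.6) |
| 3.1 | 0.5 | 37% | 4.92 (1.6) | 4.44 (1.4) |
| 3.1 | 0.7 | 51% | 4.26 (1.4) | 3.95 (1.3) |
| 4.2 | 0 | 48% | 5.89 (1.4) | 5.44 (1.3) |
| 4.2 | 0.5 | 60% | 5.35 (1.3) | 5.05 (1.2) |
| 4.2 | 0.7 | 77% | 4.80 (1.1) | 4.64 (1.1) |

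Hand check of the first row: the later 12 patients are unselected, so the estimate at 47 should be near (35/47) × 5.52 + (12/47) × 3.1 = 4.11 + 0.79 = 4.90, against 4.89 simulated.

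**The case against.** The strongest reply is that 13.8.7 does not instruct anyone to test HADS at 0.05. It asks an independent committee to fix its rules beforehand, and choosing an interim level is part of doing so. A DSMC document outside the protocol may already hold a boundary. The surrounding text also leans away from a routine efficacy look: the stated purpose is safety and missingness, questionnaire data go to the committee pooled, 13.8.3 reserves early stopping for a very surprising finding, and 9.2 keeps the analysing biostatisticians blinded. On a generous reading, 13.8.3 means only that the protocol itself fixes no rule, which would be compatible with the DSMC setting one.

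Much of this stands. It makes 8.3% a worst case for a single look, and inflation a possibility and not a prediction. It also makes the ambiguity about half a minor one: 45 of 90 is again half the information, and even 45 against a final 70 moves the worst case only from 8.3% to 7.8%.

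It does not close the gap. Blinding and pooled reports are not a boundary, and an efficacy stop cannot be triggered without comparing arms. Whatever rule the DSMC adopts, the final test needs a matching level, and neither 11.2 nor 11.4.1 makes room for one. The DSMC table in 13.8.2 lists two transplant physicians and two psychologists but no biostatistician, so the choice of boundary should not be left implicit. If the interim really is for safety and missingness alone, the efficacy clause is a mistake and should go.

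**Conclusion.** The concern holds and needs correcting. The plan names an efficacy stop, sets no interim level, boundary or adjusted final level, and contradicts itself on whether stopping rules exist. With one look at half the information and the final test at two-sided 0.05, overall type I error lies between 5.0% and 8.3%, depending on the rule the DSMC sets. It stays near 5% under a strict boundary and reaches the top of the range only if the interim is tested at an unadjusted 0.05. Further unblinded looks, which 13.8.3 does not exclude, could take it higher. After a favourable stop on an unadjusted look, the mean estimate would be 1.1 to 1.8 times the truth.

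The error range assumes a two-sided test (inferred from the 35 per arm) and a single look. The exaggeration range also rests on the assumed correlations and on the assumed 47 patients. The omission and the contradiction depend on none of these assumptions.

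**What to change.** Preferred: make 13.8.7 a safety and missingness review with no between-arm test of HADS, delete the efficacy clause, and state two-sided 0.05 for the final test in 11.4.1. This costs no power.

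Alternative, if an efficacy stop is wanted: name the boundary before any by-arm look, for example O'Brien-Fleming with p < 0.0052 at half and p < 0.048 at the end. Define half as 35 evaluable patients, and carry the final level into 11.2 and 11.4.1. The power of the final test for 4.2 points falls from 79.8% to 79.3%.

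Either way, reword 13.8.3 and 13.8.7 so that they agree on whether stopping rules exist and who sets them. The documents do not say whether the interim has already taken place. If it has, record in 13.8.7 whether HADS was compared by arm and under which rule, because the final p-value cannot be interpreted without that. The whole change is wording in 11.2, 11.4.1, 13.8.3 and 13.8.7.

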
14.0 Withdrawal of Subjects

14.1 Plan for Non-Responders

Response to the intervention will be determined upon study completion (not in "real-time,"). All participants, including those on the intervention arm, will continue to receive usual care, including as-needed referrals for professional psychology services.

14.2 Early Withdrawal of Subjects

All participants may choose to withdraw from the study at any time. We will track date of discontinuation and request a brief reason to be recorded for tracking purposes. In the event of serious medical complications (or death) precluding participation, participants will be censored after 2 months of missing data. In all other cases (non-completion of surveys without serious medical complications or death), staff will continue to request surveys until 2 months following the 6-month endpoint, as described above.

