3. Positive Reframing	Recognizing negative self-talk, replacing with positive, realistic, manageable ones	
4. Meaning Making	Identifying benefits, purpose, meaning, or legacy from cancer experience	
5. Coming Together	Discussion with parents/caregiver/spouse/significant other about what was learned, what helped, what they can do to help	Parent/Caregiver/ Spouse/Significant other inclusive meeting
6. Boosters	Personal contacts and/or digital modules to practice, further develop, and track skills.	One-on-One or Digital

Note: Sessions delivered approximately every 1-2 weeks, arranged in advance in conjunction with clinic and hospital visits or can be done via phone or other web based communication (i.e., zoom, WebEx, skype, blue jeans, go to meetings, WhatsApp, etc.) (with the exception of session 1).

Feasibility and Acceptability study of PRISM Intervention. We completed a formative study of PRISM among 24 AYAs to determine the optimal content and timing of PRISM sessions. We found it to be feasible and highly valuable to AYA patients and parents.⁹³ Eighty percent of AYA participants completed the intervention and feedback was universally positive: “This was so helpful, I wish we had done this sooner,” or “I think it’s good techniques to use, definitely. I am teaching my little sister. I’m sure it can help her, too.”

PRISM Pilot RCT (clinicaltrials.gov NCT 02340884). Next, in a phase II RCT testing PRISM efficacy among AYAs with new or recurrent cancer, we refined processes of enrollment, randomization, implementation, and data collection. We completed our target enrollment ahead of schedule; enrollment rates were 78%.

Attrition (20%) was similar on the PRISM and usual care arms, and primarily due to medical complications.

[figure not shown]
The primary objective of the phase II RCT was to assess patient-reported resilience. Final analyses suggest PRISM improved patient reported resilience and quality of life, and reduced psychological distress (Table 2).

Table 2. Mixed linear model estimates of change in instrument scores associated with PRISM compared to usual care in phase II RCT

Outcome (instrument)	Beta (95% CI)	p-value
Resilience (CDRISC-10)	3.0 (0.5, 5.4)	0.02
Generic Quality of Life (PedsQL SF-15)	7.2 (-0.8, 15.2)	0.08
Cancer-specific Quality of Life (PedsQL Cancer)	9.6 (2.6, 16.7)	0.01
Global Psychological Distress (Kessler-6)	-2.1 (-4.1, -0.2)	0.03

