Patient (and parent) reported outcomes (PROs) will be measured with the Resilience in Pediatric Cancer Assessment (RPCA), a comprehensive survey comprised of age-appropriate validated instruments (**Table 5**). The RPCA was designed with AYA and parent stakeholders to capture patient-reported outcomes associated with resilience resources.³⁰ We have successfully used it in several of our prior studies.^{29,30,90-92,99} The survey includes embedded validated instruments as well as standard demographics (age, sex, and race/ethnicity, education, income, number of children in the home).

The full RPCA survey will be administered to patients and parents at baseline, month 3 and month 6 (**Figure 3**). In order to optimize engagement, parents in both arms of the study will be asked to complete the abbreviated Resilience in Pediatric Cancer Assessment (aRPCA) at months 1, 2, 4, and 5. The aRPCA will assess only cost-consequences, as described below. In the rare case that a patient is their own money manager, AYA patients will be asked to complete cost-consequence questionnaires at each month in lieu of parents. RPCA and aRPCA surveys will be administered via REDCap or pencil-and-paper, depending on participant preference. If administered via REDCap, participants will be sent an email containing the survey link. Email language will include all text described in the IRB-approved template (see “PRISM BMT Survey letter – REDCAP”) though additional personalized text may be included to reflect participants’ specific needs. Paper-and-pencil surveys will be delivered in-person or via mail. If patients or parents specifically request to opt-out of aRPCA surveys (i.e., cost consequences assessments), study staff will no longer administer aRPCA surveys for the remainder of the study. In these cases, patients/parents will remain eligible to complete RPCA surveys.

For those on the non-intervention arm of the study, staff will schedule a “study check-in” visit to coordinate the aRPCA completion and thank families for their continued participation. If patients and parents have not completed any interval study questionnaires, we will still invite them to complete the 6 month questionnaire regardless of how many intermediate questionnaires they have completed. If patients and parents

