are reluctant to fill out the full RPCA at 3 month and/or 6 months, we will offer a shortened RPCA assessing the primary outcomes only. If patients are still reluctant to complete the questionnaire due to length, we will provide a HADS only questionnaire option. Patients and parents will be given up to 4 weeks to complete the 6 month questionnaire before deemed 'off study'.

In both arms of the study, if any participant declines to complete the full RPCA survey and/or if participants or family members report participants are unable to complete the survey due to illness complications, staff will offer in the following order: (a) an in-person (English-speaking, interview based) survey session, and (b) abbreviated version (primary outcome only – HADS questionnaire only) of the questionnaire for patients to complete. Only in cases where participants are too ill to provide self report in writing or interviews, staff will offer abbreviated versions of the survey for parents to complete as proxy respondents. These proxy questionnaires would be the patient questionnaire given to the parent to complete on behalf of their child. In such cases of proxy-completion of surveys, staff will note this distinction in the database and proxy-completion will be included as a potential confounding variable in subsequent analyses. These options will be offered in an effort to collect full data for primary endpoint assessment.

Participants in both arms of the study will be scheduled for their surveys at the time of enrollment and then reminded 1 week and 2 days prior to each survey due-date.

Participants will be contacted in person, by phone, email, text or mail to receive their RPCA/aRPCA surveys. If we have not received a response within a day of initial contact, participants will receive up to 4 follow-up phone calls, texts or emails (approximately once weekly) within a 28 day window before and after surveys are due. Follow-up surveys not received within 28 days of their due-date will be considered missing.

Participants will remain eligible for subsequent survey completion and follow-up even if surveys are missing and the same procedures will be conducted for each survey due-date.

Table 5. Resilience in Pediatric Cancer Survey Domains

AYA Surveys	Anxiety & Depression: Hospital Anxiety and Depression Scale (HADS) ¹
	Symptom Burden: Memorial Symptom Assessment Scale (MSAS) ²
	Quality of Life: PedsQL Generic Core and Cancer Modules (PedsQL) ^{3,4}
	Hope: Hope Scale ⁵

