14.3 When and How to Withdraw Subject

In this intention-to-treat analysis plan, all participants who fill out a baseline survey will be included in analyses. As above, withdrawal will be determined by study staff only in the event of medical complications or death.

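### Section 14.2 stops survey follow-up of participants too ill to take part after an undefined 2 months, against section 9.7, so month-6 HADS scores can be lost avoidably because of illness

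*Combined protocol and SAP*

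**What the plan says.** Section 14.2 (Early Withdrawal of Subjects) separates non-completers by health. The first rule opens "In the event of serious medical complications (or death) precluding participation" and continues "participants will be censored after 2 months of missing data". For everyone else, "staff will continue to request surveys until 2 months following the 6-month endpoint, as described above". Section 14.3 adds that "withdrawal will be determined by study staff only in the event of medical complications or death".

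Section 9.7 (RPCA Survey) contains no exception for health. It states: "Participants will remain eligible for subsequent survey completion and follow-up even if surveys are missing". On the month-6 survey it says "we will still invite them to complete the 6 month questionnaire regardless of how many intermediate questionnaires they have completed", although that sentence sits in a paragraph that opens with the control arm. For participants who decline the full survey or cannot complete it because of illness, it lists an interview, then a HADS-only form. For those too ill to self-report, "staff will offer abbreviated versions of the survey for parents to complete as proxy respondents", with proxy completion recorded in the database. The stated purpose is full data for the primary endpoint.

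Section 9.7 also closes the month-6 questionnaire after 4 weeks and treats follow-up surveys more than 28 days late as missing. Section 11.4.1 makes total HADS at 6 months the primary outcome, analysed by regression.

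**The concern.** The primary outcome is a single score at month 6. A rule that stops asking one group of living participants before that point, and selects the group by illness, makes missingness depend on health. Scores from seriously ill patients who can answer again by month 6 are the ones that would best inform the missing-data methods in section 11.7. Sections 9.7 and 14.2 tell site staff different things about these patients, so sites may act differently.

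Medical illness is also the likely main source of loss. Section 2.1.2 reports 20% attrition in the phase II trial, "primarily due to medical complications", and section 11.2 assumes 20% here.

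**Working it through.** **1. The plan's own figures (section 11.2).** Inputs: SD 6.2, difference 4.2, 80% power, 5% type I error (two-sided assumed), 90 randomised, 20% attrition.
- Per arm: n = 2 × (1.96 + 0.84)² × 6.2² / 4.2² = 34.2, rounded up to 35, as stated. Power at 35 per arm is 80.9% by the normal approximation and 79.8% by noncentral t.
- Attrition: 0.20 × 90 = 18 lost and 72 left, against the 70 needed.

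The planning figures reproduce. The 18 is expected loss from all causes, including death and non-medical dropout. It does not count patients affected by section 14.2.

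**2. The two sections side by side.**

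| Question | Section 14.2 / 14.3 | Section 9.7 |
|---|---|---|
| Illness precludes participation and surveys are missed | Censored after 2 months of missing data; staff may withdraw | Still eligible for later surveys; interview, HADS-only or parent proxy offered |
| Other non-completers | Asked until 6 + 2 = month 8 | Month-6 survey closes at 4 weeks/28 days, about month 7 |
| Start of the 2 months | Not stated | Not applicable |
| Meaning of censoring for a month-6 regression outcome | Not stated | Term not used |

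Section 14.2 refers back to something described above for its 2-month extension, but section 9.7 describes only 4 weeks or 28 days.

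**3. The calendar.** Patient HADS is due at months 0, 3 and 6. Take a patient who misses month 3 because of complications.
- Clock from the due date: 3 + 2 = month 5, before the primary assessment.
- Clock from the close of the 28-day window (about 0.9 month): 3 + 0.9 + 2 = 5.9, about month 6.

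Under the first reading the patient is out before month 6. Under the second, censoring coincides with the survey and the outcome depends on how the site counts.

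**4. When this would bias the comparison.** Let f be the share of an arm lost to the rule, and D the amount by which the mean month-6 HADS of those lost exceeds that of those observed. The observed arm mean is then off by −f × D. The PRISM-minus-control difference is off by f(control) × D(control) − f(PRISM) × D(PRISM). This is zero when the shares are equal and D is the same in both arms, that is, when the treatment effect is the same in patients lost and patients observed. The documents give neither f nor D for this trial, so no numbers are put in.

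**The case against.** The strongest reply is that section 14.2 covers only complications that preclude participation. Read with section 9.7, it can be a residual rule, applied after interview, HADS-only form and parent proxy have all failed. Section 9.7 then gives the general rule and 14.2 a specific exception, and the censoring term may be only a status label. That limits the point: a reader might infer that everyone with a serious complication is dropped, and the qualifier rules that out. It does not remove the conflict. Section 14.2 neither requires the section 9.7 options to be exhausted nor provides for a fresh approach at month 6, and being unable to answer around month 3 does not settle month 6. The contrast with continued requests in all other cases suggests that requests to this group stop.

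A reader might also infer that a patient who recovers by month 6 will certainly not be asked. That holds only if the clock starts at the month-3 due date, which the text does not say.

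The most tempting stronger reading is that the rule biases the treatment effect by some number of HADS points. The documents do not support it. Section 2.1.2 reports that phase II attrition was similar in the two arms, which is the only evidence on differential loss and points away from bias. Equal loss is not guaranteed here: section 15 leaves staff unblinded, staff judge what precludes participation, and section 9.4 gives the PRISM arm booster contacts every other week. That makes unequal loss possible without quantifying it.

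Finally, section 11.7 names medical complications and death as causes of missing data and provides imputation or weighting where missing at random is plausible, with sensitivity analyses otherwise. Section 9.6 records illness covariates that could support those models. This softens the consequence, but modelling cannot replace scores that were never requested. Nor does section 11.7 refer to the 14.2 rule.

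**Conclusion.** The conflict between sections 14.2/14.3 and 9.7 is real and should be resolved. As written, the plan permits avoidable, illness-related loss of the primary outcome among living, consenting patients. It leaves the start of the 2 months and the meaning of censoring undefined, and it gives two different month-6 windows (2 months in 14.2; 28 days or 4 weeks in 9.7).

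The size is unknown. The documents give no rate of serious complications in this trial and no share of such patients who could answer at month 6. Outcomes after death are missing under any rule and are not part of this point. Any loss may already lie within the planned 20%, so no power shortfall is claimed. Bias in the arm comparison would need unequal loss between arms or a different effect in sicker patients; neither is shown.

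**What to change.** - In section 14.2, end survey follow-up only at death or withdrawal of consent.
- State that every living, consenting participant is offered the month-6 HADS, whatever was missed earlier, by the routes already in section 9.7: full survey, HADS-only, interview, or parent proxy flagged as proxy in the data.
- Delete the censoring term, or define it: which missing data start the 2 months, from what date, and how the participant enters the month-6 regression.
- Align sections 14.2 and 14.3 with section 9.7, with one month-6 window for all participants.

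The cost is protocol wording and a few extra contacts using existing procedures. The downside is a small burden on ill patients, who may decline.
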